5.4.2.3. Other toxicities

For the first occurrence of any nonhematologic Grade 2 chemotherapy-related toxicity (except alopecia), all study treatment should be withheld until the toxicity recovers to Grade 1 or baseline. Treatment may then be resumed at the same dose level. For the second occurrence of any nonhematologic Grade 2 chemotherapy-related toxicity (except alopecia), treatment should be resumed at a reduced dose level following recovery of the toxicity to Grade 1 or baseline; for the third occurrence, the dose should be reduced to Dose Level 2. A fourth occurrence will lead to discontinuation of carboplatin, etoposide and topotecan treatment. For Grade 1 toxicities, the dose should not be reduced.

For any Grade 3 or 4 chemotherapy-related toxicity not mentioned above, all study treatments should be withheld until the toxicity recovers to Grade 1 or baseline. Treatment should then be resumed at the first appearance with the first dose reduction and at the second appearance with the second dose reduction. A third occurrence will lead to discontinuation of carboplatin, etoposide and topotecan treatment.

The above chemotherapy drug dose adjustment regimen is recommended by the study. If the investigator recommends different treatments in clinical practice, the investigator may select the adjustment regimen by referring to the corresponding package insert of chemotherapy drugs or clinical routine guidelines. In this case, it is necessary to clearly record the reasons for other adjustment regimens in the subject 's case and discuss with the sponsor if necessary.

5.5. Criteria for discontinuation from study treatment or withdrawal

5.5.1. Criteria for discontinuation of study treatment

A subject should discontinue study treatment if any of the following occur:

1. Disease progression, except for subjects who, in the investigator 's judgment, still benefit from the study (e.g., pseudoprogression);

- 2. To reach the maximum treatment time specified in the protocol;
- 3. Subject is pregnant;

4. Poor compliance of subjects, such as failure to receive medication and examinations as required, failure to comply with the restrictions on lifestyle during the study, and use of other prohibited concomitant medications, which have a significant impact on the evaluation of study drugs;

5. Initiation of new anticancer therapy;

6. Occurrence of an adverse event that, in the judgment of the investigator, makes it inappropriate to continue treatment with study drug;

7. The investigator considers that study treatment should be discontinued in the best benefit of the subject;

8. The subject or his/her legal representative (only applicable if the subject is not fully capable of civil conduct) requests termination of treatment.

Subjects who discontinue study treatment should complete the items specified in the trial flow chart and should be followed up according to the protocol.

5.5.1.1. Dose interruption and termination of trilaciclib

For adverse events of special interest defined in Protocol Section 8.9, refer to Investigator 's Brochure Section 6 .2 to determine whether to stop the infusion or interrupt t rilaciclib treatment. Adverse events of special interest for which no action was given in the Investigator 's Brochure were handled as defined below:

- Other Toxicity Events: For severe (Grade 3) other toxicity events, hold Trilaciclib until the event recovers to ≤ Grade 1 or baseline, then consider resuming Trilaciclib; if Grade 3 events recur, permanently discontinue Trilaciclib. Trilaciclib was permanently discontinued for life-threatening (Grade 4) other toxicities.
- Hepatotoxicity: refer to treatment for "other toxic reactions" above.
- Embolic/Thrombotic Events, Venous: if related to the injection site, refer to Chapter 6 .2, "Injection site reaction/phlebitis/thrombophlebitis" of the Investigator 's Brochure; if not related to the injection site, refer to "Other toxicities" as described above.

5.5.2. Criteria for early withdrawal

Subjects could withdraw from the study at any time for any reason. The investigator may decide whether or not to withdraw a subject from the study based on actual clinical circumstances. Criteria for early withdrawal from the study were:

1. Withdrawal of consent by the subject or his/her legal representative (only applicable if the subject himself/herself does not have full civil capacity);

2. Subject lost to follow-up.

Subjects who withdrew early were not to undergo any subsequent follow-up and assessments.

5.5.3. Handling of study treatment discontinuation or early withdrawal

When a subject discontinues study treatment or prematurely withdraws, the reason for discontinuation/early withdrawal (the primary reason should be provided if there are multiple reasons) should be documented in the original medical record and CRF, and unused study drug must be counted and returned. When the subject is lost to follow-up, the investigator should make every effort to reach out to the subject (telephone, mail/letter, contact relatives and friends according to registered information) and record these processes in the relevant documents.

5.5.4. Criteria for early termination of the study

The study may be terminated prematurely at any time if agreed to by the investigator and the sponsor in the best benefit of the subject and for reasonable medical or ethical reasons. During termination, the sponsor and investigator will ensure that adequate consideration is given to protecting the subject 's interests.

Criteria for early termination of this study were:

- 1. Significant safety risk for the study drug in the opinion of regulatory authorities, ethics committees, sponsors or investigators;
- 2. Identify major defects in the study protocol, or major deviations or human errors during

the implementation of the study, which seriously affect the quality of the trial and make it difficult to achieve the purpose of the study;

3. The sponsor may terminate the study for any scientific, medical or ethical reason, but shall fully consider the rights, safety and health of the enrolled subjects;

4. Other reasons that, in the judgment of the sponsor or investigator, make continuation of the study inappropriate.

Hematopoietic growth factors, transfusions, or platelet transfusions were prohibited within 1 week prior to the Screening blood tests.

Any diagnostic, therapeutic or surgical procedures performed during the study should be documented. Documentation will include information on dates, indications for use, procedure instructions, and any clinical or pathologic findings. Medications will be coded using the latest World Health Organization (WHO) Drug Dictionary version.

6. Pharmacokinetics

PK pharmacokinetics will be investigated in this study.

6.1. Collection, processing and storage of biological samples

6.1.1. PK Blood Sample Collection and Processing

6.1.1.1. PK blood sample collection time

6.1.1.1.1. Pharmacokinetic evaluation (Part I)

In the first part of this study, PK blood samples will be collected at the following time points.

When chemotherapy regimen is carboplatin combined with etoposide (EC regimen):

Cycle 1 Day 1:

Within 0.5 h before the start of the first Trilaciclib infusion, immediately after the end of infusion ($\pm 2 \text{ min}$, at the end of administration, excluding the flushing time, the same below), and 0.5 h $\pm 2 \text{ min}$, 1 h $\pm 5 \text{ min}$, 2 h $\pm 5 \text{ min}$, 4 h $\pm 5 \text{ min}$, 6 h $\pm 5 \text{ min}$, 8 h $\pm 5 \text{ min}$, and 12 h $\pm 10 \text{ min}$ after the end of infusion.

Cycle 1 Day 2:

Within 0.5 hours prior to the second Trilaciclib dose (24 hours \pm 30 min after the end of the first Trilaciclib infusion).

Cycle 1 Day 3:

Within 0.5 h prior to the start of the third Trilaciclib dose, immediately after the end of infusion ($\pm 2 \text{ min}$, excluding flushing time), and 0.5 h $\pm 2 \text{ min}$, 1 h $\pm 5 \text{ min}$, 2 h $\pm 5 \text{ min}$, 4 h $\pm 5 \text{ min}$, 6 h $\pm 5 \text{ min}$, 8 h $\pm 5 \text{ min}$, and 12 h $\pm 10 \text{ min}$ after the end of infusion.

Cycle 1 Day 4:

24 h \pm 30 min after the end of the third Trilaciclib infusion.

A total of 20 blood sampling points, venous blood is collected to determine the concentration of Trilaciclib in blood samples, and pharmacokinetic analysis is performed based on the test results.

When the chemotherapy regimen is topotecan:Version No.: V1.4, March 21, 2022Confidential

Cycle 1 Day 1:

Within 0.5 h prior to the start of the first Trilaciclib dose, immediately after the end of infusion ($\pm 2 \text{ min}$, excluding flushing time), and 0.5 h $\pm 2 \text{ min}$, 1 h $\pm 5 \text{ min}$, 2 h $\pm 5 \text{ min}$, 4 h $\pm 5 \text{ min}$, 6 h $\pm 5 \text{ min}$, 8 h $\pm 5 \text{ min}$, and 12 h $\pm 10 \text{ min}$ after the end of infusion.

Cycle 1 Day 2:

Within 0.5 hours prior to the second Trilaciclib dose (24 hours \pm 30 min after the end of the first Trilaciclib infusion).

Cycle 1 Day 3:

Within 0.5 hours prior to the third Trilaciclib dose.

Cycle 1 Day 4:

Within 0.5 hours prior to the fourth Trilaciclib dose.

Cycle 1 Day 5:

Within 0.5 h prior to the start of the fifth Trilaciclib dose, immediately after the end of infusion ($\pm 2 \text{ min}$, excluding flushing time), and 0.5 h $\pm 2 \text{ min}$, 1 h $\pm 5 \text{ min}$, 2 h $\pm 5 \text{ min}$, 4 h $\pm 5 \text{ min}$, 6 h $\pm 5 \text{ min}$, 8 h $\pm 5 \text{ min}$, and 12 h $\pm 10 \text{ min}$ after the end of infusion.

Cycle 1 Day 6:

24 h \pm 30 min after the end of the fifth Trilaciclib infusion.

A total of 22 blood sampling points, venous blood is collected to determine the concentration of Trilaciclib in blood samples, and pharmacokinetic analysis is performed based on the test results.

6.1.1.1.2. Pharmacokinetic evaluation (Part II)

In the second part of this study, PK blood sample collection is planned to be performed at the following time points, and the actual blood collection points could be adjusted according to the pharmacokinetic study results in the first part.

In all subjects, venous blood is collected at 4 blood sampling points on Cycle 1 Day 1 immediately after the end of Trilaciclib/placebo infusion (excluding flushing time) \pm 5 min, 0.5 h \pm 10 min, 5 h \pm 1 h after the end of infusion, and within 1 h before Trilaciclib/placebo administration on Cycle 1 Day 2 to determine the concentration of Trilaciclib in blood samples for pharmacokinetic analysis according to the test results.

6.1.1.2. Handling and storage of pk blood samples

Please refer to the laboratory manual.

7. Study evaluation

7.1. Evaluation of bone marrow protection

Assessment of myeloprotection will be based on the following: dynamic changes in complete blood counts; hematological toxicities, including febrile neutropenia and resulting infections; red blood cell and platelet transfusions; use of hematopoietic growth factors; systemic antibiotic use; dose reduction and discontinuation of chemotherapy.

Duration of severe neutropenia (DSN) in Cycle 1 was selected as the primary endpoint for efficacy evaluation. The overall protective effect of trilaciclib on each bone marrow cell line will also be comprehensively assessed through the evaluation of secondary endpoints, particularly key secondary endpoints (including SN occurrence, occurrence of red blood cell transfusions on/after Week 5, granulocyte colony-stimulating factor use rate, composite endpoints-major adverse hematologic event, etc.).

7.2. Safety evaluation

7.2.1. Clinical laboratory tests

Blood samples for hematology, urinalysis, and blood chemistry will be collected according to the trial flow chart and analytical testing will be completed at a local laboratory.

- Blood routine: white blood cell (WBC), red blood cell (RBC), hemoglobin (Hb), platelet (PLT), hematocrit (HCT), neutrophil (NEU), eosinophil (EOS), basophil (BAS), monocyte (MON), lymphocyte (LYM), etc.;
- Urinalysis: urine protein, urine pH, urine ketone body, urine glucose, urine red blood cells, urine white blood cells, etc. Note: 24-hour urine protein quantification is required for subjects with urine protein ≥ ++;
- Blood biochemistry: aspartate aminotransferase (AST), alanine aminotransferase (ALT), γ-glutamyltransferase (γ-GT), lactate dehydrogenase (LDH), cholesterol (TC), triglyceride (TG), total bilirubin (TBIL), direct bilirubin (DBIL), total protein (TP), albumin (ALB), alkaline phosphatase (ALP), creatine kinase (CK), glucose (GLU), uric acid (UA), blood urea nitrogen (BUN)/urea (Urea), creatinine (Cr), sodium (Na), potassium (K), calcium (Ca), phosphorus (P), magnesium (Mg) and chloride (Cl);
- Serum pregnancy test (females of childbearing potential only), For female subjects of childbearing potential, serum pregnancy test will be performed before the start of administration. After negative results of pregnancy test in the screening period, reliable contraceptive measures should be started;

Note: Females who were not of childbearing potential were permanently sterilized

(hysterectomy, bilateral oophorectomy, or bilateral salpingectomy) and postmenopausal. A woman ≥ 50 years of age was considered postmenopausal if she had been amenorrheic for 12 months prior to the planned date of randomization and had no other medical etiology. A woman < 50 years of age is considered postmenopausal if she has been amenorrheic for 12 months or more after stopping exogenous hormone therapy and has follicle-stimulating hormone (FSH) levels in the postmenopausal range.

• Virology:

Hepatitis B and C screening were performed during the screening period, five items of hepatitis B: if hepatitis B surface antigen (HBsAg) was positive or hepatitis B core antibody (HBcAb) was positive, HBV-DNA should be added; hepatitis C examination: if hepatitis C antibody was positive, HCV-RNA should be added.

The procedures and timing of these inspections are specified in the Study Flow Chart. Additional laboratory tests may be performed if clinically indicated.

Laboratory test results must be reviewed and confirmed by the investigator or qualified designee.

7.2.2. Physical examination and vital signs

The investigator or other study personnel authorized by the investigator should perform physical examinations and determine the subject 's vital signs as specified in the protocol. Physical examination included weight, height, general appearance, skin/mucous membranes, head, neck, chest, abdomen, joints of spine and limbs, and neurological examination. Height was measured at screening only. Further targeted physical examinations may be performed by the investigator based on symptoms. Vital signs include temperature, pulse, respiratory rate, blood pressure.

7.2.3. 12-lead electrocardiogram (ECG)

Standard 12-lead ECGs, including measurements of heart rate, QRS duration, and PR, QT, RR, and QTc intervals ($QTc = QT/RR^{0.33}$), should be performed using standard procedures at the study site. The timing of ECG measurements was specified in the trial flow chart. Unscheduled ECGs may be performed if clinically indicated.

7.2.4. Adverse events

Adverse events were monitored from the time of informed consent through the end of the safety follow-up period, initiation of new antineoplastic therapy, or withdrawal from the study, whichever came earliest. The investigator should record AEs experienced by each subject and

track progress. Adverse events should be graded and documented according to NCI-CTCAE version 5.0 throughout the study and during follow-up.

Details of AE assessment and recording are provided in the relevant sections.

7.3. Pharmacokinetic evaluation

The first part of the pharmacokinetic analysis included PK concentration analysis and PK parameter analysis.

Pharmacokinetic analysis will be based on PK analysis set (PKS), including all subjects who have received at least one dose of study drug and have at least one valid concentration data of the tested components after dosing. Non-compartmental methods using WinNonlin Version 6.3 or higher software were used to calculate pharmacokinetic parameters and descriptive summary analyses were provided.

Single-dose PK parameters:

Peak drug concentration (C_{max}), time to reach maximum concentration (T_{max}), terminal elimination half-life ($T_{1/2}$), area under concentration-time curve (AUC, including AUC_{0-t}, AUC_{0- ∞}), etc.

Multiple-dose PK parameters:

Time to maximum concentration (T_{max}) , time to maximum concentration at steady state $(T_{ss max})$, maximum drug concentration (C_{max}) , maximum drug concentration at steady state $(C_{ss max})$, minimum plasma concentration at steady state $(C_{ss min})$, area under the concentration-time curve (AUC, Including AUC_{0-t}, AUC_{0- ∞}, AUC_{ss}), terminal elimination half-life $(T_{1/2})$, fluctuation coefficient (DF), accumulation coefficient (R_{AC}), etc.

7.4. Population pharmacokinetic analysis was performed based on the data obtained for exploratory analysis to obtain the population pharmacokinetic profile of the drug.Antitumor efficacy evaluation

Tumor imaging evaluation was performed according to RECIST1.1.

Pre-screening imaging should include at least computed tomography (CT) or magnetic resonance imaging (MRI) of the brain, chest, abdomen, and pelvis. Unless contraindicated, IV contrast should be used and oral contrast may be used at the investigator 's discretion.

Baseline imaging was performed within 21 days prior to the first dose, every 6 ± 1 week after the first dose, or more frequently if clinically indicated. Imaging examinations should follow calendar days and should not be modified for treatment delays or terminations, and subjects who discontinue study drug treatment due to intolerable toxicity or for other reasons other than disease progression should continue to be followed for tumor assessments until disease progression, receipt of new antineoplastic therapy, withdrawal from the study, or death (whichever occurs first), and the sites examined are consistent with the sites examined at baseline.

Efficacy assessments were classified as complete response (CR), partial response (PR), stable disease (SD), progressive disease (PD), and not evaluable (NE). Confirmation of response according to RECIST 1.1 should be performed no less than 4 weeks from the date of the first documented partial response (PR) or complete response (CR). Imaging assessments for efficacy confirmation may be performed 4 weeks after response is first observed or at the next scheduled imaging time point.

If there are imaging results meeting the criteria available within 2 1 days prior to the first dose, they do not need to be repeated during the screening period.

For subjects who did not experience disease progression at the time of treatment discontinuation, radiographic tumor assessments continued as scheduled until disease progression, withdrawal of consent, start of subsequent anticancer therapy, or end of study.

8. Adverse event reporting

During this study, the investigator and his/her designated qualified personnel were responsible for detecting and recording all events observed during the course of the study that met the definition of an adverse event or serious adverse event according to the criteria and definitions in this study protocol. Investigators will evaluate adverse events, monitor the safety status of subjects and give corresponding protective measures to ensure the safety of subjects, and report according to relevant requirements.

8.1. Definitions of adverse event, serious adverse event, and suspected and unexpected serious adverse reaction

An adverse event (AE) is defined as any untoward medical occurrence in a subject administered an investigational product and which may manifest as symptoms, signs, disease, or laboratory abnormalities, but which do not necessarily have a causal relationship with the investigational product. An AE could therefore be any unfavorable and unintended sign (including an abnormal laboratory finding), symptom, or disease (new or exacerbated) temporally associated with the use of an investigational product.

Events meeting the definition of an adverse event include:

• Abnormal laboratory findings (hematology, clinical chemistry, or urinalysis) or other safety assessments (eg, electrocardiogram, radiographic scans, vital sign measurements), including those that worsened from baseline and were considered clinically significant

based on the investigator 's medical and scientific judgment (ie, not related to progression of the underlying disease).

- Worsening of a pre-existing condition, including an increase in frequency and/or severity of the condition.
- New conditions detected or diagnosed after the start of the study drug (even if they may have been present before the start of the study).
- Signs, symptoms, or clinical sequelae of a suspected drug-drug interaction.
- Signs, symptoms, or the clinical sequelae of a suspected overdose of study treatment or concomitant medication. Overdose per se will not be reported as an adverse event/serious adverse event unless it is an intentional overdose with possible suicidal/self-injurious intent. Such overdoses should be reported regardless of sequelae.

Events that do not meet the definition of an adverse event include:

- Abnormal laboratory findings or other abnormal safety assessments related to the underlying disease. However, if the investigator considers the severity to be greater than expected based on the subject 's condition, it should be considered an AE.
- Medical or surgical procedures (eg, endoscopy, appendectomy). Note that the condition leading to this procedure was an AE.
- Absence of an untoward medical event (hospitalization for social reasons and/or convenience).
- Underlying diseases or conditions present or detected at the start of the study that fluctuated daily within the expected range without apparent worsening.
- Pre-existing conditions or signs and/or symptoms not related to the study prior to the first dose of study drug. These events will be documented in the medical history section of the eCRF.
- Progressive Disease (PD): The expected progression of the disease under study occurring during the study is not recorded as an AE or SAE, nor is the sign or symptom caused by the expected disease progression recorded as an AE or SAE. If the investigator considers disease progression related to the investigational product during the study, it should be recorded as AE or reported as SAE; the death caused by disease progression during the safety follow-up period of the subject should be reported as SAE.

Definition of Serious Adverse Event

Serious Adverse Event (SAE) refers to any untoward medical occurrence such as death, life-threatening, permanent or serious disability or incapacity, hospitalization or prolongation of hospitalization required by the subject or congenital anomaly or birth defect after the subject receives the investigational product.

- Causing death
- Life Threatening

This refers to an AE in which the subject was already at risk of death at the time of the AE, and does not refer to an assumption that the AE, if more severe, could have caused death.

• Persistent or significant disability or incapacity

The AE results may cause serious inconvenience or interference with the subject 's normal life and activities.

• Requires hospitalization or prolongation of hospitalization

The AE caused the subject to be hospitalized for treatment or had already been prepared to be discharged, but prolonged hospitalization due to an adverse event; it was necessary to be clear that the cause of the condition was due to the adverse event rather than admission for elective surgery, non-medical reasons, etc.

• Congenital anomaly or birth defect

The offspring of the subject presents with malformation or congenital functional defect.

• Other important medical events

Medical and scientific judgment must be exercised in deciding whether expedited reporting is appropriate in other situations, such as important medical events that may not be immediately life-threatening, fatal, or hospitalised, but medical action to prevent one of the above situations is also usually considered serious. For example, important treatment in the emergency room or allergic bronchospasm at home, cachexia or convulsion without hospitalization, drug dependence or addiction.

When it is unclear whether the SAE is considered, the investigator should discuss with the sponsor and the Ethics Committee.

Definition of suspected and unexpected serious adverse reaction

Suspected Unexpected Serious Adverse Reaction (SUSAR) refers to a suspected and unexpected serious adverse reaction whose nature and severity of clinical manifestations exceed those in the Investigator 's Brochure (IB) of the investigational product, the package insert of the marketed drug or the summary of product characteristics.

8.2. Time period and frequency for collecting adverse event and serious adverse event information

AE collection: In this study, AEs will be collected from the time the subject signs the informed consent form to the time point specified in the trial flow chart, in which the medical events occurred unrelated to the study intervention from the time of signing the informed consent form to the first medication should be recorded in the CRF as medical history/concomitant diseases, rather than the AE part.

Investigators were not required to actively collect AEs or SAEs following the subject 's safety follow-up period. However, if the investigator learns of any SAE, including death, at any time after a participant leaves the study, and considers the event to be reasonably related to the study intervention or study participation, the investigator must promptly collect a report.

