10.3.6. Safety analysis

Safety analyses will be based on the Safety Analysis Set. Safety evaluations included monitoring of treatment emergent adverse events (TEAEs), physical examinations, vital sign measurements, electrocardiograms (ECGs), and clinical laboratory tests (hematology, blood chemistry, and urinalysis) throughout the treatment period.

Descriptive statistics will be used to analyze adverse events, laboratory test indicators, vital signs and ECG, and summarized according to the treatment groups actually received.

Extent of exposure will be summarized as duration of treatment and dose of study drug taken during the treatment period.

According to the vital signs data at baseline and each visit time point, each indicator of vital signs at each visit time point and the change from baseline were statistically summarized.

According to the laboratory test results at baseline and each visit time point, the results of laboratory test items completed at each visit time point and the positive and abnormal changes from before treatment were statistically summarized.

Only treatment-emergent adverse events were counted. A TEAE was defined as an untoward medical occurrence that emerged during treatment or worsened relative to pretreatment. All AEs will be coded according to the International Conference on Harmonisation (ICH) Medical Dictionary for Regulatory Activities (MedDRA) and the number and incidence will be summarized by System Organ Class (SOC), Preferred Term (PT) and investigational product grouping. List the serious adverse events after medication, adverse

events leading to drug withdrawal, adverse events leading to dropout and drug-related adverse events, and describe the details of each adverse event/adverse reaction in each subject in a separate table, including the type, severity, occurrence and duration, outcome of adverse events as well as their relationship with the investigational drug and the dose of the drug.

Concomitant medications will be reported using summary tables.

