4.6.2. Adverse Events

Adverse events will be monitored from the time of informed consent through the end of the safety follow-up period, initiation of new antineoplastic therapy, or withdrawal from the study, whichever comes first. Adverse events will be graded and recorded according to NCI-CTCAE version 5.0 throughout the study and during follow-up.

Only treatment-emergent adverse events (TEAEs) will be summarized. A TEAE is defined as any untoward medical occurrence or an adverse event that worsened relative to pretreatment state that emerged newly from the first dose of study drug through 30 days after the last dose or before the start of new anticancer therapy. AE will be coded according to the International Conference on Harmonisation (ICH) Medical Dictionary for Regulatory Activities (MedDRA) and the number and incidence will be summarized by System Organ Class (SOC) and Preferred Term (PT). Serious adverse events after medication, adverse events leading to dose reduction, delay or discontinuation, adverse events leading to dropout, adverse events leading to death, adverse events of special interest, drug-related adverse events, etc. will be summarized separately, and the details of each adverse event for each patient will listed, including the type, severity, occurrence and duration, outcome of adverse events, and the relationship with the study drug.

For summarizing TEAE, the incidence of adverse events will be calculated based on the number of patients with adverse events rather than the number of adverse events. When calculating the number and percentage of patients with adverse events, one patient with multiple occurrences of the same adverse event will only be counted one.

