5.2. Appendix 2 Test Flow Sheet

	Screenin	n (21 days per cycle, 6 cycles)										Safety Visit ^b	Survival
	g Period			Cy	cle 1			C	Cycle 2 a	nd abov	e	~~~y + 1510	Follow-up ^c
	D-21 ~ - 1	D1	D2	D3	D8	D10	D15	D1	D2	D3	D8	+ 30 days	Every 60 days
Window (Days)					±1	±1	±1	± 3			± 1	± 7	± 7
Informed Consent	Х												
Demographic information	Х												
Past medical history ^d	Х												
Checked in/out	Х												
Randomization (Part II only)	Х												
ECOG	Х	Х						Х				Х	
Physical examination	Х				Х		Х	Х				Х	
Body height ^e	Х	Х						Х					
Vital signs	Х				Х			Х				Х	
Biochemistry ^f	Х				Х		Х	Х			Х	Х	
Hematology ^g	Х	Х		Х	Х	Х	Х	Х			Х	Х	
Urine test ^h	Х							Х			Х	Х	
12-lead ECG	Х									Х			
Serum Pregnancy ⁱ	Х												
Tumor assessment ^j	X	Imaging every 6 ± 1 week after first study								drug do	se		
PK (Part I) ^k			Par	t I D1-4 I	Blood san	npling							

Line 1 ES-SCLC Patient Study Flow (EC Protocol)

Protocol Number: B02B0	0801-TRILA-3	01			Jiangsu S	imcere Pha	armaceutica	l Co., Ltd					
	Screenin g Period			C	ן (21 d ycle 1	Freatmen ays per o	it Period cycle, 6 cy	a vcles)	Cycle 2 a	and abov	/e	- Safety Visit ^b	Survival Follow-up °
	D-21 ~ - 1	D1	D2	D3	D8	D10	D15	D1	D2	D3	D8	+ 30 days	Every 60 days
Window (Days)					± 1	± 1	±1	± 3			± 1	± 7	± 7
PK (Part II) ^k			Part I	I Day 1-	2 Blood s	ampling							
Trilaciclib/Placebo ¹		Х	X	Х				X	Х	Х			
Carboplatin ¹		Х						Х					
Etoposide ¹		Х	Х	Х				Х	Х	Х			
Virology ^m	Х												
AEs	Х	Х	Х	Х	Х	Х	Х	Х	Х	Х	Х	X	
Concomitant medication	Х	Х	Х	Х	Х	Х	Х	Х	Х	Х	Х	X	
Survival and other anti- tumor conditions	.11.1	1 • • •	1: 01				••••	1 '1'	1				X

a. Trilaciclib + EC chemotherapy will be administered in 21-day cycles until disease progression, intolerability, or discontinuation of treatment at the investigator 's discretion (eg, 6 cycles of chemotherapy have been completed).

b. Follow-up was performed 30 days (± 7 days) after the last dose, starting a new anticancer therapy (-7 days), or withdrawing from the study (-7 days), whichever came first.

c. Survival follow-up refers to telephone follow-up every 60 days (± 7 days) after the last dose to collect other anti-tumor information until 50% of subjects die.

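### The last scheduled adverse-event assessment may fall on Day 23 after the last dose, while the SAP counts TEAEs to Day 30

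*Protocol*

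**What the plan says.** **Collection.** Protocol 7.2.4: "Adverse events were monitored from the time of informed consent through the end of the safety follow-up period", or to new antineoplastic therapy or withdrawal if either comes earlier. Protocol 8.2 ties the end to the flow chart: "AEs will be collected from the time the subject signs the informed consent form to the time point specified in the trial flow chart". In Tables 11 and 12 the last AE mark stands in the safety-visit column, headed + 30 days with a window of ± 7. The survival follow-up column has no AE mark. After the safety follow-up period, 8.2 says "Investigators were not required to actively collect AEs or SAEs following the subject 's safety follow-up period".

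**Visit timing.** SAP Appendix 2, footnote b: "Follow-up was performed 30 days (± 7 days) after the last dose". The same footnote brings the visit forward for a new anticancer therapy or study withdrawal (each with − 7 days), whichever comes first. The flow tables of Protocol V1.4 carry the same ± 7, although the SAP was written for V1.3.

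**Counting.** SAP 4.6.2 counts as treatment-emergent an event that "emerged newly from the first dose of study drug through 30 days after the last dose or before the start of new anticancer therapy". The Protocol's own definition, in 10.3.6, sets no day limit: "A TEAE was defined as an untoward medical occurrence that emerged during treatment or worsened relative to pretreatment". The 30-day limit therefore comes from the SAP alone.

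**The concern.** Collection and counting end at different times. Collection ends at a visit whose date can move by a week either way. Counting ends on a fixed day, or earlier at new therapy. If the visit comes early, the SAP still accepts events up to Day 30, but nobody is scheduled to ask about them.

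SAP 4.6.2 bases incidence on the number of patients with an event, and SAP 4.11 does not impute missing data unless otherwise specified. A patient seen early therefore contributes nothing for the uncovered days, as if they had been event-free. Safety and tolerability is a secondary objective of Part II. With about 40 patients per arm, one patient whose only event of a given type is missed changes that arm's incidence by 1/40 = 2.5 percentage points.

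**Working it through.** **Inputs**
- Safety visit: 30 days after the last dose, window ± 7 (Protocol Tables 11 and 12; SAP Appendix 2, footnote b).
- End of the TEAE window: Day 30 after the last dose, or start of new anticancer therapy (SAP 4.6.2).
- Last dosing day of a cycle: Day 3 for EC, Day 5 for topotecan (Protocol 5.2, Table 4).

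**1. Is the ± 7 what the SAP works with?** SAP Appendix 4 ends the safety-visit laboratory window 40 days (first line) or 42 days (second/third line) after the first dose of the last cycle. Nominal day + last dosing day + window gives 30 + 3 + 7 = 40 and 30 + 5 + 7 = 42. Both agree.

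**2. Permitted visit days.** 30 − 7 = Day 23 to 30 + 7 = Day 37.

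**3. Uncovered days.** Gap = max(0, 30 − visit day).
- Visit on Day 23: 7 days, or 7/30 = 23% of the 30 days after the last dose.
- Visit on Day 24: 6 days. Day 27: 3 days. Day 29: 1 day.
- Visit on Days 30 to 37: 0 days.

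**4. Average gap, by assumption only.** The documents give no distribution of visit dates. If visits were spread evenly over the 15 permitted days, 7/15 = 47% would fall before Day 30, and the mean gap would be (7+6+5+4+3+2+1)/15 = 28/15 = 1.87 days, or 6% of the 30 days. Visits clustered at Day 30 would give less.

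**5. Against the whole TEAE window.** The window runs from the first dose. For EC without delays (assumption):
- Six cycles: last dose on Day 5 × 21 + 3 = 108, window ends on Day 138. Maximum gap 7/138 = 5%; even-spread mean 1.87/138 = 1.4%.
- Four cycles: last dose on Day 3 × 21 + 3 = 66, window ends on Day 96. Maximum 7/96 = 7%; mean 1.87/96 = 1.9%.

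**6. Withdrawal.** Protocol 5.5.2 allows no follow-up after early withdrawal, and SAP 4.6.2 does not close the TEAE window there. A patient who withdraws on Day w after the last dose leaves 30 − w days uncovered, which exceeds a week when w is below 23.

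**7. With a 30 (+ 7) window.** The earliest visit after the last dose is Day 30, so the maximum gap in step 3 becomes 0.

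**The case against.** The best counter-argument is that the safety follow-up period has no stated end date. It could be read as a fixed 30 days, with ± 7 as scheduling tolerance only. That reading closes the gap on paper. However, 8.2 points to the flow chart, whose last AE mark is the visit, and no AE contact is scheduled after an early visit. Tumour imaging continues every 6 ± 1 weeks in patients without progression (Protocol 7.4), so a site may hear of events by chance, but that is not planned collection.

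Three stronger conclusions are tempting and not supported:
- *A reader might infer that an SAE on Days 24 to 30 is reported only if judged related.* The condition that the investigator "considers the event to be reasonably related to the study intervention or study participation" applies in 8.2 after a participant leaves the study. A patient who has had the safety visit and entered survival follow-up has not left. Protocol 8.6 has the investigator report any SAE learned of, related or not, and 8.7 requires it within 24 hours of awareness.
- *A reader might infer that the SAP reports a 30-day post-treatment incidence.* It does not. Day 30 limits which recorded events count, and incidence covers the whole period from the first dose. The 23% and 6% describe only the tail after the last dose.
- *A reader might take 47% as the expected share of early visits.* It rests on an even spread that nothing in the documents supports. It also ignores patients who start new therapy before Day 30, for whom the TEAE window closes as well.

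It also stands that a symmetric visit window is ordinary practice, that the safety analysis is descriptive, and that no formal test is affected.

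**Conclusion.** The mismatch is real and small. For patients seen before Day 30 who neither withdraw nor start new anticancer therapy, up to 7 days of the SAP's TEAE window have no scheduled active collection. Seven days is the maximum, and visits on Days 30 to 37 leave no gap. What can be missed is non-serious AEs and SAEs that never reach the site. The likely result is a slight under-count of late TEAEs, expected to be similar in both arms because the visit rule is the same for both. The primary endpoint and sample size are untouched. This rests on reading the safety visit as the end of the safety follow-up period, which follows from 8.2 and the flow chart but is not stated outright. It is worth correcting because the correction is nearly free.

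**What to change.** - Change the after-last-dose window from 30 (± 7) to 30 (+ 7) days in Protocol Tables 11 and 12, their footnote b, and SAP Appendix 2. The 40- and 42-day limits in SAP Appendix 4 stand, because the upper side does not move.
- Keep both earlier triggers in footnote b. New therapy also closes the TEAE window in SAP 4.6.2. Withdrawn patients cannot be seen later, so their trigger is needed as well.
- State in SAP 4.6.2 that the TEAE window also closes at withdrawal.

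The change removes the gap for patients who neither withdraw nor start new therapy. The − 7 days attached to the two earlier triggers, read as a visit up to a week beforehand, can still leave up to 7 days uncovered in those patients. The cost is slightly less scheduling freedom for sites, with no additional visit.
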